4.2 INCLUSION CRITERIA

1. Males or females, between 18 and 75 years of age, inclusive.
2. a) Patients on therapeutic doses of Ursodeoxycholic acid (UDCA) for ≥ 12 months and stable therapy for ≥ 3 months prior to enrolment.
OR
b) Patients who are unable to tolerate UDCA, and did not receive UDCA for at least 3 months from the date of screening.
3. History of confirmed Primary Biliary Cholangitis Diagnosis, based on American Association for the Study of Liver Disease [AASLD] and European Association for Study of the Liver [EASL] Practice Guidelines; [Lindor 2009; EASL 2009], as demonstrated by the presence of at least ≥ 2 of the following 3 diagnostic factors:
 - History of elevated Alkaline Phosphatase levels for at least 6 months prior to Screening Visit 1
 - Positive antimitochondrial antibodies (AMA) titer or if AMA negative or in low titer ($<1:80$) PBC specific antibodies (anti-GP210 and/or anti-SP100 and/or antibodies against the major M2 components [PDC-E2, 2-oxo-glutaric acid dehydrogenase complex])
 - Liver biopsy consistent with PBC.

4. ALP $\geq 1.67 \times$ upper limit of normal (ULN) at Visit 1 and Visit 2 and with $< 30\%$ variance between the levels from Visit 1 to Visit 2.
5. Contraception: Female patients must be postmenopausal, surgically sterile, or if premenopausal, agree to use ≥ 1 effective method of contraception during the trial. Effective methods of contraception are considered to be Hormonal (e.g., contraceptive pill, patch, intramuscular implant or injection); or Double barrier method, i.e., (a) condom (male or female) or (b) diaphragm, with spermicide; or Intrauterine device (IUD); or Vasectomy (partner).
6. Must provide written informed consent and agree to comply with the trial protocol.

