4.3 EXCLUSION CRITERIA

1. Consumption of >3 units of alcohol per day (>21 units per week) if male and >2 units of alcohol per day (>14 units per week) if female for at least 3 consecutive months in the last 5 years (Note: 1 unit = 12 ounces of beer, 4 ounces of wine or 1 ounce of spirits/hard liquor).
2. History or presence of other concomitant liver diseases including:
 - Hepatitis B or C virus (HCV, HBV) infection
 - Primary sclerosing cholangitis (PSC)
 - Alcoholic liver disease
 - Definite autoimmune liver disease or overlap syndrome
 - Non-alcoholic steatohepatitis (NASH)
3. Cirrhosis with complications, including history or presence of: spontaneous bacterial peritonitis, hepatocellular carcinoma, bilirubin $> 2 \times$ ULN, ascites, encephalopathy, known esophageal varices or history of variceal bleeding and active or history of hepatorenal syndrome.
4. History of any venous thromboembolism, TIA, intracranial hemorrhage, neoplasm, arteriovenous malformation, vasculitis, bleeding disorder, coagulation disorders or screening blood tests that indicate altered coagulability (e.g. platelet count, aPTT, PTT or TT tests).
5. Patients with INR $>$ ULN at visit 1.

6. Patients with total bilirubin > ULN at visit 1 that is not due to Gilbert's syndrome.
7. Patients with >30% increase in ALT, total bilirubin, or INR between Visit 1 to Visit 2, unless both results (visit 1 and visit 2) are within the reference range.
8. Patients with serum creatinine >ULN according to the gender at Visit 1.
9. Patients with abnormal total creatine kinase (CK) OR lipase OR amylase at Visit 1.
10. Unstable cardiovascular disease, including:
 - unstable angina, (i.e., new or worsening symptoms of coronary heart disease within the past 3 months), acute coronary syndrome within the past 6 months, acute myocardial infarction in the past 3 months or heart failure of New York Heart Association class (III – IV) or worsening congestive heart failure, or coronary artery intervention, within the past 6 months
 - history of (within prior 3 months) or current unstable cardiac dysrhythmias
 - uncontrolled hypertension (systolic blood pressure [BP] >160 mmHg and/or diastolic BP >100 mmHg)
 - stroke or transient ischemic attack within the prior 6 months
11. History of malignancy in the past 5 years and/or active neoplasm with the exception of resolved superficial nonmelanoma skin cancer.

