4.4.1 Discontinuation of Subject Investigational Product (IP)

Patients with worsening liver function will not be enrolled in the study. Evidence of worsening liver function will be assessed based on the 2 initial laboratory values used to establish the baseline.

Elevations in ALT and/or AST, occurring after the initiation of study drug, that meet the definition of a potential Case of Drug-Induced Liver Injury per below;

1. If patients with abnormal baseline liver indices develop elevations of AST or ALT greater than 2x baseline or total bilirubin greater than 1.5x baseline values while on study, testing shall be repeated within 48 -72 hours.
2. If there are persistent elevations in ALT or AST greater than 2x baseline or TBL greater than 1.5x baseline values, then close observation (testing and physical examination 2-3 times per week) shall be initiated or study drug will be discontinued
- A decision to discontinue or temporarily interrupt the study drug will be considered based on factors that include how much higher baseline ALT and AST were relative to the upper limit of normal (ULN) and how much the on study ALT and AST levels have increased relative to baseline, in addition to

whether there is concomitant elevation of bilirubin or INR. Study drug will be discontinued or temporarily interrupted:

- a. When the baseline values were < 2x ULN, discontinue if ALT or AST increases to > 5x baseline,
- b. When the baseline values were \geq 2x ULN but < 5x ULN, discontinue if ALT or AST increases to >3x baseline,
- c. When the baseline values were \geq 5x ULN, discontinue if ALT or AST increases to > 2x baseline,
- d. Discontinue if ALT or AST increase > 2x baseline AND the increase is accompanied by a concomitant TBL increase to >2x baseline OR the INR concomitantly increases by >0.2,
- e. In any patients with signs and symptoms of fatigue, nausea, vomiting, right upper quadrant pain or tenderness, fever, rash, and/or eosinophilia (> 5%).

- If a patient lives in a remote area, laboratory testing can be performed locally and the results shall be promptly communicated to the investigator site promptly.
- If patient develops an adverse event of grade 3 that is probably or possibly related to study drug and any patient regardless of attribution to drug who develops a grade 4 or higher Common Terminology Criteria for Adverse Event (CTCAE version 4.03).

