- Parameters of renal function: IP is to be discontinued if the estimated glomerular filtration rate (eGFR) falls to <60 mL/min/1.73m² (calculated using Chronic Kidney Disease Epidemiology Collaboration (CKD-EPI) equation) and where the value is reconfirmed after 24 hrs repeat. Additionally, any subject who requires renal replacement therapy will also have IP discontinued.
- Patient will be immediately discontinued from study drug and followed until resolution of adverse event and laboratory values have returned to baseline, if any of the following criteria occur.

- a. TB \geq 3.0 mg/dL in individuals with normal baseline TB. In individuals with elevated baseline TB due to known Gilbert's syndrome, doubling of direct bilirubin will prompt immediate discontinuation of the study drug.
- b. Total CK $>$ 5x ULN
- c. Amylase and lipase $>$ ULN
- d. Hemoglobin $<$ 100 g/L or HCT $<$ 30%
- e. Platelets $<$ 100000/ μ L
- f. WBC $<$ 3.5 X 10⁹/L
- g. If more than 3 patients develop a CTCAE grade 3 or higher in the same category, or if 3 or more patients meet the above individual criteria (a to f) the trial may be stopped and/or unblended safety data will be evaluated.

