6.1.2 Secondary Endpoints

1. To compare the effect of Saroglitazar magnesium (2 mg and 4 mg) and placebo on below mentioned parameters following a 16-week treatment:
 - i. Change from baseline in ALP at Week 4, Week 8, Week 12 and Week 16 in Saroglitazar magnesium as compared to placebo.
 - ii. Change from baseline in lipid profile (TG, TC, HDL, LDL, and VLDL) at Week 4, Week 8, Week 12 and Week 16 in Saroglitazar magnesium as compared to placebo.
 - iii. Change from baseline in liver biochemistries (GGT, ALT, AST, Bilirubin and albumin) at Week 4, Week 8, Week 12 and Week 16 in Saroglitazar magnesium as compared to placebo.
 - iv. Change from baseline in serum total bile acids, at Week 4, Week 8, Week 12 and Week 16 in saroglitazar as compared to Placebo.
 - v. Change from baseline in 7 α -hydroxy-4-cholesten-3-one (C4) at Week 16 in saroglitazar as compared to Placebo.
 - vi. Change from baseline in fibroblast growth factor 19 (FGF 19) at Week 16 in saroglitazar as compared to Placebo.
2. Proportion of patients with ALP improvement, i.e. 15%, 20%, 30%, 40% and normalization at Week 8 and Week 16.
3. Change in QoL at Week 16 by using PBC40.
4. Change from baseline in ALP in patients who are unable to tolerate UDCA at week 16 in Saroglitazar 2 mg and 4 mg as compared to Placebo.
5. Safety and tolerability of Saroglitazar magnesium 2 mg and 4 mg.
6. Pharmacokinetics of Saroglitazar.

**Zydus Discovery
DMCC**

CLINICAL TRIAL PROTOCOL

Saroglitazar Magnesium – Phase II

SARO.16.004

CONFIDENTIAL

PAGE 47 OF 82

Pharmacokinetics of Saroglitazar Magnesium will be performed in patients with PBC. The samples will be collected at Pre-dose (0.0), 0.5, 1.0, 2.0, 3.0, 4.0, 6.0, 8.0, 10.0 and 24 hours post-dose on Visit 3 and Visit 7. In addition, pre-dose sample will be collected at Visits 4, 5, and 6.

The following pharmacokinetic parameters will be evaluated:

- i. Peak Plasma concentration (Cmax)
- ii. Time to reach peak Plasma concentration (Tmax)
- iii. Area under Plasma concentration vs. time curve till the last time point (AUC0-t)
- iv. Area under Plasma concentration vs. time curve extrapolated to the infinity (AUC0- ∞) after first dose
- v. Area under plasma concentration vs. time curve in a 24 h dosing interval (AU τ)
- vi. Elimination rate constant (λ_z)
- vii. Elimination half-life (t_{1/2})
- viii. Apparent Volume of distribution (Vd/F)
- ix. Apparent Clearance (CL/F)
- x. Minimal or Trough plasma concentration (C_{min}) -for last dose only

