7 INVESTIGATIONAL PLAN

7.1 STUDY DESIGN AND PLAN

This is a Phase 2 prospective, multicentre, randomized, double-blind, placebo-controlled study includes a total 36 patients with a diagnosis of Primary Biliary Cholangitis. The study will be conducted over a period of up to 26 weeks and will include a 6-week Screening Phase, a 16-week Treatment Phase and a safety follow-up visit after 4 weeks.

Screening Phase:

- Visit 1 (Day -42): Patient eligibility for participation in the study will be assessed. Medical history will be obtained and physical examination, electrocardiogram (ECG) and laboratory evaluations (including serology, [anti-nuclear antibody, smooth muscle antibody and serum immunoglobulin level G], clinical chemistry, hematology, liver biochemistries, and urinalysis) will be performed. In patients with ANA or SMA antibody positive titers, a liver biopsy must have been performed to rule out autoimmune hepatitis or overlap syndrome. Female patients will undergo a pregnancy test. Serum ALP must be ≥ 1.67 upper limit of normal (ULN) to proceed further in the study.
- Visit 2 (Day -14 to -7): Liver biochemistries (ALT, ALP, total bilirubin (TB) and INR will be re-measured approximately 4 weeks from Day -42 to determine eligibility. Elevated ALP must be ≥ 1.67 ULN on 2 occasions in the Screening Phase and is necessary for study entry. If there is an increase of more than 30% in the levels of ALT, total bilirubin or INR at Day (-14) to Day (-7) [Visit 2] as compared to the values on Day (-42) [Visit 1], then such patients will not be eligible for study entry. The average of two assessments (Visit 1 and Visit 2) of liver biochemistries and INR will be considered as baseline values for these parameters.

Randomization & Treatment Phase:

- Visit 3: The Randomization & Treatment Phase will include 6 outpatient visits over a period of 16 weeks, including the randomization visit. Patients will be randomly assigned to receive either Saroglitzaz magnesium (2 mg or 4 mg) or placebo orally

once daily in addition to their ongoing treatment with UDCA (Patients unable to tolerate UDCA will receive only the investigational medicinal products), starting on Day 1 and continuing for 16 weeks. Efficacy and safety parameters will be assessed during each study visit as per the Schedule Visit Table 1.

- Visit 3.1: Patient will visit study site at 2 weeks after randomization visit for LFTs. The LFTs will be performed at local laboratory.

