7.6 DATA MONITORING COMMITTEE

Safety data including adverse events and liver-related events (i.e., clinically meaningful elevations in liver biochemistries ALT, AST, and bilirubin) will be reviewed regularly by a Data Monitoring Committee. The Data Monitoring Committee will have a formal structure and will operate according to a previously agreed upon remit.

Approved by:
[name]

Protocol No. SARO.16.004
Version No.: 6.0

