9.4.4 Events of Clinical Interest

Selected non-serious and serious adverse events are also known as Events of Clinical Interest (ECI) and must be reported within 24 hrs to CRO/Sponsor Clinical Safety following the same procedures as outlined in Section 9.4.2. Sponsor Contact information can be found in the Investigator Trial File Binder (or equivalent).

An elevated AST or ALT lab value that is greater than or equal to 3X the upper limit of normal and an elevated total bilirubin lab value that is greater than or equal to 2X the upper limit of normal and, at the same time, an alkaline phosphatase lab value that is less than 2X the upper limit of normal, as determined by way of protocol-specified laboratory testing or unscheduled laboratory testing.*

*Note: These criteria are based upon available regulatory guidance documents. The purpose of the criteria is to specify a threshold of abnormal hepatic tests that may require an additional evaluation for an underlying etiology.

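### The only liver Event of Clinical Interest requires concurrent ALP below 2 x ULN, but entry requires ALP of at least 1.67 x ULN with no ceiling, so 24-hour reporting of an ALT/AST-plus-bilirubin rise depends on the patient's ALP

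*Protocol*

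**What the plan says.** Protocol 9.4.4 lists a single laboratory-based ECI, to be sent to CRO/Sponsor Clinical Safety within 24 hours whether or not the event is serious. It joins three conditions: ALT or AST at least 3 x ULN, total bilirubin at least 2 x ULN and, "at the same time, an alkaline phosphatase lab value that is less than 2X the upper limit of normal". A note says that the criteria follow regulatory guidance and mark test results that may need further work-up for a cause. The only other ECI is an overdose without an adverse event (Table 4 in 9.4.3).

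Inclusion criterion 4 (4.2) asks for ALP of at least 1.67 x "upper limit of normal (ULN) at Visit 1 and Visit 2 and with" less than 30% variance between them. Section 7.1 repeats that ALP must reach this level "on 2 occasions in the Screening Phase and is necessary for study entry". Nothing in 4.2 or 4.3 caps ALP. Exclusion criterion 6 (4.3) removes "Patients with total bilirubin > ULN at visit 1 that is not due to" Gilbert's syndrome, so outside that condition a bilirubin of 2 x ULN is normally new on study.

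**The concern.** In this trial a raised ALP is an entry condition. An ALP of 2 x ULN or more at the time of a liver event may simply be the patient's usual level, and it does not show that a new ALT/AST-plus-bilirubin rise is cholestatic. Under 9.4.4 it still removes the event from 24-hour reporting.

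Two consequences follow. The patients left out are those with the highest ALP. And because eligibility moves with ALP, which the drug is meant to lower, the same event would be an ECI more often on an effective drug than on placebo. That direction does not flatter the drug, but which events reach sponsor safety as ECIs should not depend on the primary efficacy variable. Late notice can also matter later: the 7-day and 15-day regulatory clocks in 9.4.3 run from the sponsor's first knowledge.

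**Working it through.** The plan gives no figure to reproduce. The check compares thresholds, then follows the other reporting routes, then sizes the gap under stated assumptions.

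**1. Same event, different ALP.** Two patients each have ALT 4 x ULN and bilirubin 2.5 x ULN. With ALP 1.9 x ULN the event is an ECI due in 24 hours. With ALP 2.0 x ULN it is not an ECI.

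**2. Which starting ALP can qualify.** Let B be the starting ALP (x ULN) and f the fractional fall by the time of the event. The ALP clause is met if B(1 - f) < 2, that is B < 2/(1 - f). The falls are those the protocol uses in 6.1.2: "Proportion of patients with ALP improvement, i.e. 15%, 20%, 30%, 40% and normalization at Week 8 and Week 16".

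| Fall f | Limit 2/(1 - f) | Starting ALP must be below |
|---|---|---|
| 0 | 2/1.00 | 2.00 x ULN |
| 15% | 2/0.85 | 2.35 x ULN |
| 20% | 2/0.80 | 2.50 x ULN |
| 30% | 2/0.70 | 2.86 x ULN |
| 40% | 2/0.60 | 3.33 x ULN |

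Read the other way, f must exceed 1 - 2/B: 20% from 2.5 x ULN, 33% from 3, 50% from 4 and 60% from 5. This step needs no assumed distribution.

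**3. Other routes for an ALT/AST-plus-bilirubin rise, none with an ALP condition.**

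- 4.4.1 stopping rule: "Discontinue if ALT or AST increase > 2x baseline AND the increase is accompanied by a concomitant TBL increase to >2x baseline", or an INR rise above 0.2. It governs dosing and sets no reporting clock.
- 4.4.1 trial-level rule (g): "if 3 or more patients meet the above individual criteria (a to f) the trial may be stopped". It needs several patients.
- 7.6: "Safety data including adverse events and liver-related events" are reviewed regularly by the committee, with no 24-hour duty.
- 6.2: all adverse events are notified to the sponsor, with no time limit.
- 9.4.2: reporting within 24 hours, but only if the event is judged serious.

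For an event not judged serious with ALP at or above 2 x ULN, no route has a 24-hour clock.

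**4. Size, under assumptions.** The documents give no ALP distribution. Assume lognormal ALP before screening with median 1.3, 1.6, 1.9 or 2.2 x ULN and log-SD 0.4, 0.5 or 0.6; within-patient log-SD 0.15; and no effect of the injury itself on ALP. Simulate 2,000,000 candidates per combination, keep those with both screening values at least 1.67 x ULN and within 30% of each other, and take baseline as their mean.

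| Quantity | Range over the grid |
|---|---|
| Baseline ALP at least 2 x ULN | 67-89% |
| Later ALP below 2 x ULN, no drug effect | 15-40% |
| Later ALP below 2 x ULN, after a 15% fall | 29-65% |
| Later ALP below 2 x ULN, after a 30% fall | 47-86% |
| Ratio able to qualify, 15% fall to no effect | 1.6-2.0 |
| Ratio able to qualify, 30% fall to no effect | 2.2-3.2 |

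Of 36 patients, 67-89% is about 24 to 32 (0.67 x 36 = 24.1; 0.89 x 36 = 32.0).

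Sensitivity:

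- Log-SD 0.25: baseline share 46-82%; ratios 1.4-2.0 (15% fall) and 1.6-3.2 (30% fall).
- Within-patient log-SD 0.10-0.20 at the grid corners: baseline share 64-90%; ratios 1.5-2.2 and 2.0-3.5.

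**The case against.** The strongest reply is that patients are already protected and only timing is missing. Outside Gilbert's syndrome, Visit 1 bilirubin is at most ULN, and a Visit 2 value above ULN can be at most 30% higher, so the averaged baseline is at most (1.0 + 1.3)/2 = 1.15 x ULN. A bilirubin of 2 x ULN is then at least 2/1.15 = 1.74 times baseline. That is above the 1.5-fold trigger in 4.4.1 for repeat testing within 48-72 hours, with close observation or discontinuation if it persists. Bilirubin of 3.0 mg/dL or more with a normal baseline means immediate discontinuation. Under 6.2.2 a result that needs more diagnostic tests or changes dosing meets the adverse-event criteria, and 6.2 then requires sponsor notification. All of this stands. It narrows the gap to the missing 24-hour clock for events not judged serious.

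The size figures also count patients who could qualify, not events missed. If 0.5-3% of 36 patients had such an event (an assumed rate), that is 0.2 to 1.1 events in the whole trial. The results also move with the assumptions: an injury that itself raised ALP by 20% would cut the 15-40% share to about 5-15%. Both points are fair; the second makes the gap wider.

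The ALP clause is deliberate and rests on guidance, and dropping it gives up some specificity. But the note's stated purpose is to prompt a search for cause. Where everyone enters with raised ALP, the clause blocks that prompt for patients whose ALP has not changed. Finally, the committee's remit is not in the documents and may define its own liver alerts. That cannot be checked, and 7.6 does not say so.

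**Conclusion.** The point holds. As written, a patient whose ALP is at or above 2 x ULN at the event cannot trigger the liver ECI, whatever the ALT, AST and bilirubin. This follows from the text of 9.4.4 and 4.2 and from the cut-offs of 2.00, 2.35, 2.86 and 3.33 x ULN, with no assumed distribution. Under the assumed distributions a majority of entrants start in that position, though with a tight spread it can be just under half.

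The consequence is limited. It concerns expedited reporting of events not judged serious. The SAP plans no ECI table, so no planned comparison is biased, and few such events are likely in 36 patients over 16 weeks. The change is still worth making: the gap is in safety reporting, it falls on the patients with the highest ALP, and it is cheap to close.

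**What to change.** In 9.4.4, make concurrent ALT or AST of at least 3 x ULN and total bilirubin of at least 2 x ULN reportable to CRO/Sponsor Clinical Safety within 24 hours regardless of ALP. Record the concurrent ALP on the report to help judge cause, and align the safety-plan wording.

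As a useful but not essential addition, SAP 8.3.5 could include one listing and one by-arm table of patients who meet the ALT/AST and bilirubin parts, with concurrent ALP shown. The planned listings and shift tables do not bring the two elevations together, although in a trial of this size a reader could assemble them.

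The cost is one sentence, the matching safety-plan text and, if wanted, one listing and one table. The downside is a few more 24-hour reports, some of which will reflect PBC progression or Gilbert's syndrome and not drug injury.

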9.4.5 Expected Adverse Events

Adverse events reported by 2% or more patients treated with Saroglitazar magnesium during the double-blind, active-controlled trial with Pioglitazone as the comparator regardless of causality included gastritis and asthenia. In the double-blind placebo controlled study, AEs reported by 2% or more patients treated with Saroglitazar magnesium included gastritis, dyspepsia, pyrexia and pain. The details of AE experienced during the Saroglitazar magnesium studies are mentioned in IB.

9.4.6 Pregnancy

At screening every female subject of childbearing potential will be tested for serum pregnancy test. Women are advised not to become pregnant during the trial and for at least 4 weeks \pm 3 days after the end of treatment period. Adequate contraceptive measures shall be taken to prevent pregnancy. Even when contraceptive methods are used, there is a small risk that pregnancy might occur. In case a subject becomes pregnant, then she will be withdrawn from the trial and adequate monitoring of the subjects will be conducted.

**Zydus Discovery
DMCC**

CLINICAL TRIAL PROTOCOL

Saroglitazar Magnesium – Phase II

SARO.16.004

CONFIDENTIAL

PAGE 73 OF 82

Although pregnancy and lactation are not considered adverse events, it is the responsibility of Investigators or their designees to report any pregnancy or lactation in a subject (spontaneously reported to them) that occurs during the trial or within 4 weeks±3 days of completing the treatment period. All subjects who become pregnant must be followed to the completion/termination of the pregnancy. Pregnancy outcomes of spontaneous abortion, missed abortion, benign hydatidiform mole, blighted ovum, fetal death, intrauterine death, miscarriage and stillbirth must be reported as serious events (Important Medical Events). If the pregnancy continues to term, the outcome (health of infant) must also be reported.

The investigator should report the pregnancy to CRO/Sponsor Clinical Safety within 24 hours of being notified. CRO/Sponsor Clinical Safety will then forward the Exposure In Utero form to the investigator for completion.

